during the maintenance regimen at the discretion of the treating physician only after discussion with the PI. Patients will receive Ipilimumab starting on day 1 and every 6 (or 12) weeks (+/-3 days) there after. The plan is to give a total of 4 doses of the ipilimumab at 6 (or 12) week intervals and then stop therapy. Patients who have evidence of budding relapse or seem to have clinical benefit may continue the ipilimumab every 6 (or 12) weeks.

Arm 2 includes a salvage cohort and a frontline AML >/= 65 years age cohort. The salvage cohort of vidaza+nivolumab+ipilimumab will have 66 slots and will the priority protocol in salvage setting as the vidaza+nivolumab has already completed enrollment of 70 patients and has no additional slots. The frontline cohort of vidaza+nivolumab+ipilimumab and vidaza+nivolumab will be open simultaneously and we will enroll alternately to these two frontline protocols with close monitoring for futility and toxicity as specified in the predefined statistical efficacy and futility stopping rules in Statistics Section 11.0. This will allow us to closely assess differences in efficacy and toxicity among these two protocols in a similar patient population.

- **Arm 3 (Vidaza + Nivolumab + Venetoclax):** Patients will receive therapy with nivolumab IV infusion on Day 8 and Day 22 (+/-3 days) of each 5-azacytidine cycle for first 4 cycles or until CR (whichever occurs earlier) followed by a maintenance regimen (one dose of nivolumab on Day 8 of each cycle of 5-azacytidine). Patients who have evidence of budding relapse or seem to have clinical benefit may continue or revert back to receiving nivolumab on Day 8 and day 22 (+/-3 days) of each cycle of 5-azacytidine. Patients may receive nivolumab more or less frequently during the maintenance regimen at the discretion of the treating physician only after discussion with the PI. Venetoclax will be administered orally daily on Days 1-21 of the first cycle; and Days 1-14 or Days 1-21 for subsequent cycles based on response achieved and degree of myelosuppression as described later in the protocol.

Arm 3 includes a part a lead-in phase (n=6-18) followed by part b expansion in two cohorts: a salvage cohort (n=30) and a frontline cohort AML >/= 65 year age cohort (n=30) (see inclusion 4.2.1 for detailed eligibility to these cohorts).

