- Arm 3: Azacytidine will be administered subcutaneously (SQ) or intravenously (IV) for 7 days of every cycle with daily schedule of 7 consecutive days (Days 1-7) or for days 5-2-2 which is 5 consecutive weekdays (Days 1-5) with rest on the 2 weekend days (Days 6 and 7) and then dosing the first two weekdays of the next week (Days 8 and 9) of each 28-day cycle as determined by treating physician. Alternative dosing schedules such as 4-2-3 which is 4 consecutive weekdays (Days 1-4) with rest on the 2 weekend days (Days 5 and 6) and then dosing the first three weekdays of the next week (Days 7, 8, and 9) of each 28-day cycle or other schedules allowing the 2 day weekend interruption may be applied as long as we make every attempt to give the 7 days of azacytidine as consecutively as possible. This must be clearly documented in the medical record as determined by treating physician after approval from the PI. Both SQ and IV forms of administration are FDA approved and considered interchangeable. Patients may start receiving 5-azacytidine by one route and changed to the other, and also administration schedules from one schedule and changed to the other at any time as needed based on patient and/or physician preference.

Nivolumab will be administered as an approximately 60 minute IV infusion on Day 8 and Day 22 (+/- 3 days) of each 5-azacytidine cycle for the first 4 cycles or until CR (whichever occurs earlier) followed by a maintenance regimen (one dose of nivolumab on Day 8 of each cycle of 5-azacytdine).

Patients who have evidence of budding relapse or seem to have clinical benefit may continue or revert back to receiving nivolumab on Day 8 and Day 22 (+/-3 days) of each cycle of 5-azacytidine. Patients may receive nivolumab more or less frequently during the maintenance regimen at the discretion of the treating physician only after discussion with the PI.

Nivolumab will be administered every cycle with no interruptions unless there are adverse events as described in Section 5.3.

Venetoclax will be administered orally daily on Days 1-21 of the first cycle; and Days 1-14 for subsequent cycles depending on the dose level being evaluated in the lead in phase (Table 5C).

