Table 5C: Arm 3: Dose levels of 5-azacytidine, nivolumab and venetoclax during the lead-in phase (part a)

| Dose level | 5-azacytidine (mg/m ² /d, Days 1-7) | Nivolumab (mg/kg, day 8 and 22) | Venetoclax (400mg or equivalent) |
|---|---|------------------------------------|-------------------------------------|
| -2 | 75 | 1.0 | D1-14 |
| -1 | 75 | 1.0 | D1-21 |
| 0 (starting dose and target dose)) | 75 | 3.0 (starting dose) | D1-21 |

The goal of the lead-in phase is to identify the MTD i.e. the dose at which <2/6 patients experience DLT. During the lead-in phase the dose/s/duration of nivolumab and/or venetoclax may be reduced if 2 or more patients experience DLT at any given dose as shown in Table 5C. The RP2D will be selected at the end of the lead-in phase and may be the MTD dose or a dose level lower than the MTD.

Once the RP2D is decided the expansion (part b) will open in 2 cohorts: Frontline cohort (n=30) and Salvage Cohort (n=30) with eligibility as defined in 4.2.1. See “statistics” section for more details.

After the lead-in (part a) the dose of nivolumab may NOT be reduced in the expansion (part b) of the study. For potential nivolumab related AEs only dose interruptions will be permitted. Dose reductions or escalations of venetoclax and 5-azacytidine are permitted in the expansion (part b) of the study and dose reductions or escalations of 5-azacytidine or venetoclax beyond those mentioned in table 5C or 5.3.2 should be discussed with the PI and documentation of the justification recorded in the chart. Only Salvage patients as defined in Inclusion criteria 4.1B will be enrolled during in the lead-in phase.

The dose and /or schedule of administration is subject to modification pending information from ongoing clinical trials of nivolumab or ipilimumab or venetoclax as a single agent and in combination with other drugs.

DLT is defined as clinically significant non-hematologic adverse event or abnormal laboratory value assessed as unrelated to disease progression, intercurrent illness, or concomitant medications and occurring during the first cycle on study that meets any of the following criteria:

- CTCAE Grade 3 AST (SGOT) or ALT (SGPT) for ≥= 7 days or grade 3 hyperbilirubinemia for ≥= 7 days
- CTCAE Grade 4 AST (SGOT) or ALT (SGPT) of any duration
- All other clinically significant non-hematological adverse event that is Grade 3 or 4 according to the NCI common terminology criteria version 4.0 with the following exceptions:

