Patients that are removed from study before day 28 for any reason other than toxicity and have not experienced DLT will be replaced.

5.2.1.6 Arm 2: We will first treat 6 patients at dose level 0 in the lead-in phase. If DLT occurs in $>/=2/6$ patients, this dose level would exceed the MTD, and 6 patients will be treated at the next lower dose level (i.e. dose level -1). If DLT occurs in $</=1/6$ patients, this dose level would not exceed the MTD, and 6 patients will be treated at the next higher dose level (i.e. dose level +1). The dose escalation or de-escalation (Table 5b) will continue in cohorts of 6 until we reach a dose level at which $<2/6$ patients experience a DLT in the first 28 days or if $</=1/6$ patients experience a DLT at dose level +1. The highest dose level at which 0-1/6 patients experience a DLT in the first 28 days of treatment will be the MTD and will be used to treat an additional 54 salvage 1 and 2 patients (Arm 2 Salvage Cohort) and 30 frontline AML $>/= 65$ years not candidates for induction therapy (Arm 2 Frontline cohort) in the phase II portion of the study. If $>/=2/6$ patients experience DLT at dose level -2, the study will be revised to consider additional lower dose levels (based on potential synergistic toxicity).

Patients that are removed from study before day 28 for any reason other than toxicity and have not experienced DLT will be replaced.

5.2.1.7 Arm 3: We will first treat 6 patients at dose level 0 in the lead-in phase (part a). If DLT occurs in $>/=2/6$ patients, this dose level would exceed the MTD, and 6 patients will be treated at the next lower dose level (i.e. dose level -1). The dose de-escalation (Table 5C) will continue in cohorts of 6 until we reach a dose level at which $<2/6$ patients experience a DLT in the first 28 days. The dose level at which 0-1/6 patients experience a DLT in the first 28 days of treatment will be the MTD. If $>/=2/6$ patients experience DLT at dose level -3, the study will be revised to consider additional lower dose levels (based on potential synergistic toxicity).

If DLT is observed in the first 28 days of treatment in 0 or 1/6 at dose level 0, then dose level 0 will be the MTD. The RP2D will be selected at the end of the lead-in phase and may be the MTD dose or a dose level lower than the MTD.

Patients that are removed from study before day 28 for any reason other than toxicity and have not experienced DLT will be replaced.

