- Venetoclax will be administered orally daily on Days 1-21 of the first cycle; and Days 1-14 for subsequent cycles.
- In cycle 1, patients should undergo a bone marrow aspiration and biopsy on day 21 (+/- 4 days). Patients who achieve marrow remission (i.e. bone

Nivolumab and azacytidine marrow blasts <5% by morphology) or marrow aplasia/hypoplasia (</=10% cellularity or insufficient sample) should discontinue venetoclax for the remainder of the cycle and be monitored for count recovery.

- a) If the Day 21 bone marrow shows <5% blasts, the venetoclax should be held, and cycle 2 should not be initiated till ANC>0.5 and platelets are >30K without platelet transfusion support for >5 days.
- b) If the Day 21 bone marrow shows aplasia/hypoplasia (</=10% cellularity or insufficient sample), the venetoclax should be held on Day 21, and a repeat bone marrow should be performed on Day 28 (+/- 4 days) for response and MRD assessment. If the Day 28 bone marrow shows >/=5% blasts proceed with cycle 2 if this is in the best interest of the patient (those with C1D28 bone marrow >/=5% are allowed to receive 21 days of venetoclax in cycle#2). If the Day 28 bone marrow shows <5% blasts, the venetoclax should continue to be held, and cycle 2 should not be initiated till ANC>0.5 and platelets are >30K without platelet transfusion support for >5 days. If the Day 28 bone marrow shows persistent aplasia/hypoplasia (</=10% cellularity or insufficient sample) continue to hold the venetoclax and repeat a bone marrow in approximately 10-14 days.
- c) If a bone marrow remission (<5% blasts) or aplasia/hypoplasia is not confirmed on the Day 21 bone marrow, patients should continue venetoclax until day 28 and have a repeat bone marrow on Day 28 (+/- 5 days). If the Day 28 bone marrow shows >/=5% blasts proceed with cycle 2 if this is in the best interest of the patient (those with C1D28 bone marrow >/=5% are allowed to receive 21 days of venetoclax in cycle #2). If the Day 28 bone marrow shows <5% blasts or aplasia/hypoplasia follow steps outlined in "a" and "b" above.
- d) Treatment interruptions and dosing schedules other than the ones mentioned above can be considered after discussion with the PI and proper documentation of the rationale.
- e) Of note the nivolumab infusion will continue as scheduled and will not be impacted or adjusted based on venetoclax dosing schema or venetoclax related delays.

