If prolonged myelosuppression (more than 8 weeks) WITH evidence of a hypocellular marrow (marrow cellularity less than 5% without evidence of leukemia) is observed, 5-azacytidine and nivolumab OR 5-azacytidine with nivolumab and ipilimumab OR 5-azacytidine with nivolumab and venetoclax will be discontinued. Delays in start of subsequent cycles greater than 8 weeks will be acceptable only for patients who are deriving clinical benefit and after discussion with the principal investigator of potential risk/benefit ratio. If the peripheral counts do not recover (ANC <1 x10⁹/L and/or platelets <30 x10⁹/L) but there is evidence of residual leukemia in the bone marrow by morphology or flow-cytometry, subsequent cycles can be administered at the discretion of the treating physician not earlier than 21 days after the prior cycle.

5.2.2.5 For patients who discontinue therapy, the reason for treatment discontinuation will be captured.

5.2.2.6 Patients must receive at least 5 of 7 planned doses of azacitidine, 2 of 2 planned doses of nivolumab and 18 of 21 planned doses of venetoclax during the first 28 days on trial (i.e. during cycle 1) to be considered evaluable

Nivolumab and azacytidine during the DLT phase. Patients who receive less than these doses of each drug during the first 28 days on trial will not be considered evaluable during the DLT phase. However, if such patients develop a toxicity that would normally be considered a DLT this will still be captured as a DLT. Any toxicity that meets the criteria for DLT during the first 28 days of trial in a patient who has received at least one dose of either azacitidine, venetoclax or nivolumab will constitute a DLT. Patients not considered evaluable due to insufficient dosing and who do not develop a toxicity that is considered a DLT will be replaced. These patients may continue therapy on trial after discussion with the PI if they are having clinical benefit and the reasons for continuation and potential benefit/risk profile for the patient must be clearly documented in the medical records. In the expansion phase (part b), DLT will not be monitored. We will perform continuous safety monitoring every 5 patients for “drug-related non-hematological Grade 3/4 AE’s.”

5.2.2.7 Dose modifications other than the ones mentioned above can be considered after discussion with the PI and proper documentation of the rationale.

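### Arm 3 dose level -2 is a 14-day venetoclax level, but the cycle 1 schedule and the DLT-evaluability rule are both written for 21 days

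*Combined protocol and SAP*

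**What the plan says.** Table 5C (section 5.2.1.4) defines three Arm 3 lead-in levels:

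| Level | Azacitidine (mg/m²) | Nivolumab (mg/kg) | Venetoclax |
|---|---|---|---|
| 0 | 75 | 3.0 | D1-21 |
| -1 | 75 | 1.0 | D1-21 |
| -2 | 75 | 1.0 | D1-14 |

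The venetoclax column names no cycle. The text under the table says that the dose or "duration of nivolumab and/or venetoclax may be reduced if 2 or more patients experience DLT at any given dose". Section 5.2.1.7 adds: "The dose de-escalation (Table 5C) will continue in cohorts of 6", until fewer than 2 of 6 patients have a DLT in the first 28 days.

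Four other statements bear on venetoclax days:

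- **Section 5.2.1.7, bullets after the de-escalation rule:** "Venetoclax will be administered orally daily on Days 1-21 of the first cycle; and Days 1-14 for subsequent cycles". No dose level is excepted. Item c continues venetoclax to Day 28 if the Day 21 marrow shows neither remission nor aplasia. Patients with at least 5% blasts at Day 28 "are allowed to receive 21 days of venetoclax in cycle" 2. Under item d, "dosing schedules other than the ones mentioned above can be considered after discussion with the PI".
- **Section 5.2.1, Arm 3:** the same days, but with a qualifier: "Days 1-14 for subsequent cycles depending on the dose level being evaluated in the lead in phase (Table 5C").
- **Section 3.1, Arm 3:** "Days 1-14 or Days 1-21 for subsequent cycles based on response achieved and degree of myelosuppression as described later in the protocol".
- **Section 5.2.2.6:** DLT evaluability needs, among other things, at least "18 of 21 planned doses of venetoclax during the first 28 days on trial (i.e. during cycle 1"). Patients below the threshold who have no DLT are replaced. A DLT in such a patient still counts.

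**The concern.** Venetoclax days are the whole of the step from level -1 to level -2, so the text around the table has to respect them. It does not. One sentence gives 21 days in cycle 1 to everyone in Arm 3. The evaluability rule has a fixed numerator and denominator that fit levels 0 and -1 but not a 14-day level.

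What is at stake is the lead-in's ability to reach a decision at its lowest tabulated level. Finding the MTD of this triplet is a primary objective (section 1.1). The level chosen from the lead-in is carried into two expansion cohorts of 30 patients each. If level -2 is opened, the team must know how many days to give in cycle 1 and which patients count among the six.

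**Working it through.** **The plan's own figure.** Section 11.2 gives 18 lead-in patients for Arm 3. Three levels × 6 patients = 18, which matches Table 5C.

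**Size of the step in the DLT window.** With Table 5C setting cycle 1, level -1 gives 21 days and level -2 gives 14. The reduction is 21 − 14 = 7 days, and 7/21 = 33%. With the ramp in section 5.2.1.7 (100 mg, 200 mg, then 400 mg daily, no azole adjustment):

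- Level -1: 100 + 200 + 19 × 400 = 7,900 mg.
- Level -2: 100 + 200 + 12 × 400 = 5,100 mg, which is 2,800/7,900 = 35% less.

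From cycle 2 the default in section 5.2.1.7 is 14 days at both levels.

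**Evaluability at level -2.**

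- Required venetoclax doses in the first 28 days: 18.
- Maximum planned at D1-14: 14. Since 14 < 18, full compliance still fails the rule.
- A DLT-free patient is therefore non-evaluable and replaced, while a patient with a DLT is counted. Replacing patients adds none who count as DLT-free, so 0 or 1 DLT among six evaluable patients cannot be reached.
- The exception is item c. If it were taken to restart venetoclax on Days 22-28, the total would be 14 + 7 = 21, which meets 18. That route is open only to patients whose Day 21 marrow shows neither remission nor aplasia. Item c also speaks of continuing the drug, which presumes that it has not stopped.

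**Same proportion at 14 days.** 18/21 = 6/7 = 0.857, and 14 × 6/7 = 12. The equivalent rule is 12 of 14.

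**How often level -2 would be reached.** The documents give no DLT rate for Arm 3, so a range is assumed. For true rate p, the chance that a cohort fails is P(≥2 of 6) = 1 − (1−p)⁶ − 6p(1−p)⁵. If p is the same at levels 0 and -1, the chance that both fail is the square.

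| Assumed p | P(≥2 of 6) | Level -2 reached |
|---|---|---|
| 0.1 | 0.114 | 1.3% |
| 0.2 | 0.345 | 11.9% |
| 0.3 | 0.580 | 33.6% |
| 0.4 | 0.767 | 58.8% |

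Nivolumab falls from 3.0 to 1.0 mg/kg between levels 0 and -1. If the DLT rate falls with it, and p is the rate at level 0, these figures are upper values.

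**A sign that table and text were not reconciled.** Section 5.2.1.7 sends the study for revision after DLTs at dose level -3. Table 5C has no such level.

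**The case against.** The strongest reply is that a level-specific table overrides a general sentence. Section 5.2.1 refers the days to Table 5C, the text under the table makes it the guide to reductions, section 5.2.1.7 de-escalates by it, and section 5.2.2.8 carries forward the dose established from it. This stands, and it limits the point. A reader might infer from the all-levels sentence in section 5.2.1.7 that the step from -1 to -2 removes no drug, so that six more patients would receive a regimen that has just failed. The documents do not support that as the intended meaning, because these four places all point to the table. A reader might also object that a difference confined to cycle 1 makes the step trivial. It does not: DLTs are judged in the first 28 days, and later cycles are already at 14 days by default.

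The two conflicts cannot both bite. If cycle 1 were 21 days at level -2, the 18-of-21 rule would work but the level would not differ from -1 in the DLT window. If cycle 1 is 14 days, the level is distinct but the rule fails. The second case is the natural one. Another reading of section 5.2.1 lets the table set only later cycles. That would again leave the two levels alike in the DLT window.

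It would be too strong to say that 21 days after cycle 2 has no basis. The bullets under section 5.2.1.7 allow Days 1-21 when azacitidine cycles are delayed, after discussion with the PI or Co-PI. Section 5.3.2 lets the days per cycle be shortened for individual patients. What is missing is the response and myelosuppression criterion that section 3.1 promises for later cycles in general.

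In practice, investigators would probably give 14 days and count the patients sensibly, and the IND Office must approve each cohort summary before a dose level changes. Earlier lead-ins without venetoclax also showed few DLTs: 0 of 6 (section 2.3 C) or 1 of 6 (section 5.2.2.8) in Arm 1, and 0 of 12 in Arm 2 (section 2.3 D). These facts lower the chance of harm. They do not supply a rule, and discretion case by case does not define a dose level.

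**Conclusion.** The point holds and is wrong as written, not merely unstated. Level -2 in Table 5C conflicts with the cycle 1 schedule in section 5.2.1.7 and with the evaluability threshold in section 5.2.2.6. On the natural reading the first is a wording conflict. The second has a practical consequence: at most 14 doses against a required 18, so DLT-free patients at level -2 do not count unless venetoclax is resumed under item c.

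The effect depends on level -2 being used, either after two failed cohorts or because the RP2D is set below the MTD. The reach probabilities of 1.3% to 58.8% rest on assumed DLT rates of 10% to 40% that are equal at the two higher levels. No sample size, stopping boundary or operating characteristic in section 11 changes, and no effect on ORR follows.

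**What to change.** 1. Label the venetoclax column of Table 5C as cycle 1.
2. In section 5.2.1.7, exempt level -2 from the 21 days in cycle 1, and state whether item c's continuation to Day 28 applies at that level.
3. In section 5.2.2.6, scale the venetoclax threshold to the level: 18 of 21 at levels 0 and -1, and 12 of 14 at level -2.
4. Make sections 3.1 and 5.2.1 refer to the table for cycle 1 and to section 5.2.1.7 for later cycles, including the existing allowances for cycle 2 and for delayed azacitidine. If 21 days is meant to be available more widely from cycle 3, state the marrow and count criteria.

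The cost is low: one column label, one exception, one scaled number and two cross-references. No patients are added and no analysis changes.

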Two ongoing trials are evaluating VEN combination regimens in treatment naïve patients with AML who are ≥ 65 years of age and who are not eligible for standard induction: (a) to evaluate the efficacy and tolerability of the combination of VEN with a methyltransferase inhibitor (azacytidine or decitabine) (ClinicalTrials.gov Identifier: NCT02203773); (b) to evaluate VEN with low-dose cytarabine (ClinicalTrials.gov Identifier: NCT02287233).

Overview of Ongoing Phase 1b Study (M14-358): Venetoclax in Combination with HMA in Treatment Naïve AML

As of 09 March 2016, a total of 45 subjects ≥ 65 years of age with treatment naïve AML ineligible to receive standard induction therapy were enrolled into the escalation stage at 3 dose levels of venetoclax at 400 mg, 800 mg, and 1200 mg. Venetoclax was administered daily during the 28-day cycles in combination with decitabine (20 mg/m^2 intravenously on Days 1 – 5 once every 28 days) or azacitidine (75 mg/m^2 intravenously or subcutaneously on Days 1 – 7 once every 28 days). Preliminary safety and efficacy data are available from the ongoing dose escalation stage of this trial.

The most common adverse events for all subjects in Study M14-358 were nausea (53.3%), diarrhea (44.4%), febrile neutropenia (40.0%), neutrophil count decreased (31.1%), platelet count decreased, cough, and fatigue (28.9% each), edema peripheral and hypokalemia (26.7% each). Events grade 3 and above were reported for the majority (91.1%) of subjects; the most common event was febrile neutropenia (40.0%). Serious adverse events were reported for 27 (60.0%) subjects, including febrile neutropenia (11 subjects), malignant neoplasm progression (3 subjects) atrial fibrillation, abdominal pain, non-cardiac chest pain, pyrexia, pneumonia, sepsis, bone pain (2 subjects each). All other events occurred in 1 subject each. The combination of venetoclax with decitabine and azacitidine demonstrates a tolerable safety profile.

As of 09 March 2016, the ORR, as assessed by the investigators for the subjects enrolled into the 3 dose levels, was 62.2% (28 of 45), with CR in 12 (26.7%), CRI in 15 (33.3%), and PR in 1 (2.2%). Four subjects (8.9%) were reported to have morphologic leukemia-free state (less than 5% blasts in bone marrow aspirate sample with at least 200 nucleated cells) after completion of Cycle 1. Eight

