5.3.0 Dose Adjustments

Toxicity Directly Attributable to Study Drugs

Patients experiencing unacceptable toxicity directly attributable to the study drugs should temporarily stop treatment according to the guidelines in the dose adjustment schema.

5.3.1 Nivolumab, Ipilimumab, Venetoclax and 5-azacytidine dose adjustments for hematological drug- related adverse events (AE):

Dose reduction/interruption/discontinuation decisions should be based on the CTCAE version 4.0 (Appendix C) of the toxicity and the guidelines provided below.

- Patients with acute leukemia's usually present with abnormal peripheral blood counts at the time therapy is started and myelosuppression is an expected event during the course of therapy for acute leukemia's. Thus, no dose adjustments or treatment interruptions for myelosuppression

will be planned for the first 4 cycles and/or in the presence of residual leukemia. After that, treatment interruptions and dose adjustments may be considered according to the following guidelines only when there is no evidence of active leukemia (e.g., only if <5% blasts in the bone marrow by morphology or flow-cytometry or cytopenias not considered to be related to leukemia).

- Patients with a response (no marrow evidence of leukemia) and pre-cycle counts of neutrophils $>1 \times 10^9/L$ and platelets $>50 \times 10^9/L$ who have sustained low counts of neutrophils $<0.5 \times 10^9/L$ or a platelet count $<20 \times 10^9/L$ for more than 2 consecutive weeks in the current cycle, may have the treatment with 5-azacytidine and/or venetoclax interrupted at the discretion of the treating physician after discussing with the PI until neutrophils recover to $\geq 1 \times 10^9/L$ and platelets to $\geq 50 \times 10^9/L$. Nivolumab and ipilimumab have not been associated with neutropenia and/or thrombocytopenia in prior studies and should generally not be interrupted or discontinued for myelosuppression.

- If there are persistent peripheral blood blasts, or the bone marrow shows >5% blasts or evidence of leukemia by flow cytometry, treatment may be continued regardless of neutrophil and platelet count with supportive care as needed. Dose-interruptions of 5- azacytidine and/or venetoclax in these patients should be considered on an individual case and discussed with the PI.

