^hEOS visits include a physical examination, CBC with differential and platelets and a limited chemistry profile (total bilirubin, serum creatinine, SGPT or SGOT). A bone marrow aspiration may be done if non-response or progressive disease cannot be unequivocally diagnosed from peripheral blood.

Data regarding adverse events will be collected during the study. Please see **Appendix D** regarding data capturing of adverse events and adverse events source documentation.

Protocol specific data will be entered into PDMS/CORe. PDMS/CORe will be used as the electronic case report form for this protocol. Only unexpected AEs will be recorded in the Case Report Form (CRF). The Principal Investigator will sign and date the AE log per each patient at the completion of each course. Following signature, the AE log will be used as source documentation for the adverse events for attribution.

Treatment may be discontinued for a variety of reasons, including patient withdrawal, investigator decision, and reasons specified by the protocol. Reasons for discontinuation of treatments are described below.

8.1 CRITERIA FOR RESPONSE:

Response Criteria for AML

Response criteria will be modified from the International Working Group for AML [67]. Responders are patients who obtain a CR, CRI, or PR, with or without cytogenetic response, hematologic improvements, and morphologic leukemia-free state. Briefly, criteria are as follows:

8.1.1 Complete remission (CR):

- ◆ Peripheral blood counts:
 - No circulating blasts
 - Neutrophil count $\geq 1.0 \times 10^9/L$
 - Platelet count $\geq 100 \times 10^9/L$
- ◆ Bone marrow aspirate and biopsy:
 - $\leq 5\%$ blasts
 - No Auer rods
 - No extramedullary leukemia

8.1.2 Complete Remission with Incomplete Platelet Recovery (CRp):

For patients to be classified as being in CRp, they must achieve CR except for incomplete platelet recovery ($< 100 \times 10^9/L$).

8.1.3 Complete remission with incomplete blood count recovery (CRi):

- ◆ **Peripheral blood counts:**
No circulating blasts
Neutrophil count $<1.0 \times 10^9/L$, or
Platelet count $<100 \times 10^9/L$
- ◆ **Bone marrow aspirate and biopsy:**
 $</= 5\%$ blasts
No Auer rods
No extramedullary leukemia

8.1.4 Partial remission:

- ◆ All CR criteria if abnormal before treatment except:
- ◆ $>/=50\%$ reduction in bone marrow blast but still $>5\%$

8.1.5 Morphologic leukemia-free state:

- ◆ Bone marrow: $</=5\%$ myeloblasts

8.1.6 Hematologic Improvement (HI):

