Once safety of the MTD has been established, any patients still on study at a dose lower than MTD can be dose escalated up to MTD. Patients treated in the lead-in phase at MTD

will be included in the Phase II portion of the study.

The efficacy of the combination will be measured by the overall response rate (ORR), defined as CR (complete remission) + CRp (complete remission with incomplete platelet recovery) + CRi (complete remission with incomplete count recovery) + MLFS within 6 months of treatment initiation among adult patients with refractory/ relapsed AML AND newly diagnosed older patients with AML. ORR and toxicity will be monitored simultaneously using the Bayesian approach of Thall, Simon, Estey (1995, 1996) and the extension by Thall and Sung (1998).

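### A marrow with exactly 5% blasts meets the response criteria in section 8.1 but is not a marrow remission under the Arm 3 marrow rules, and in Arm 3 that one value can decide a primary-endpoint response

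*Combined protocol and SAP*

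**What the plan says.** **Response scoring (section 8.1).** CR and CRi allow marrow blasts up to and including 5%, and CRp inherits the CR criterion. MLFS has one listed criterion: "Bone marrow: $</=5\%$ myeloblasts". PR requires blasts still above 5%, as does the blast-response line in 8.1.6. Within section 8.1, exactly 5% is on the remission side.

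**Arm 3 marrow rules (section 5.2.1.7).** Marrow remission is "marrow blasts <5% by morphology". For day 21: "If a bone marrow remission (<5% blasts) or aplasia/hypoplasia is not confirmed on the Day 21 bone marrow, patients should continue venetoclax until day 28". For day 28: "If the Day 28 bone marrow shows >/=5% blasts proceed with cycle 2 if this is in the best interest of the patient". Here exactly 5% is on the other side.

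**Other places.** The hematologic DLT definition (after Table 5C) uses less than 5% for absence of residual leukemia. In section 5.3.1, one rule applies "only if <5% blasts in the bone marrow by morphology or flow-cytometry", while the next treats blasts above 5% as leukemia. On blast percentage alone, exactly 5% falls under neither of those two rules.

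**Arm 3 primary endpoint (section 11.2).** ORR is CR + CRp + "CRi (complete remission with incomplete count recovery) + MLFS within 6 months of treatment initiation". PR and hematologic improvement are not included. For Arms 1 and 2, section 11.2 includes both.

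**The concern.** The primary endpoint uses a more inclusive blast cut-off than the one by which the same protocol decides whether an Arm 3 marrow is in remission. A patient whose marrow shows 5% can be entered as an ORR responder while the marrow rules regard remission as not confirmed. Two assessors working from different sections could classify that patient differently.

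Compared with a below-5% rule, the 5%-inclusive rule can only raise ORR. Arm 3 is monitored every five patients against whole-number boundaries, so a single classification can decide whether a cohort stops or continues.

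**Working it through.** **1. The two rules side by side**

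| Marrow blasts | Marrow criterion in 8.1 for CR, CRi, MLFS | Marrow remission in 5.2.1.7 | Agree? |
|---|---|---|---|
| 4% | met | yes | yes |
| 4.9% | met | yes | yes |
| 5% | met | no | **no** |
| 5.1% | not met | no | yes |
| 6% | not met | no | yes |

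The conflict is confined to exactly 5%. (On day 21, a marrow of 10% cellularity or less, or an insufficient sample, follows rule b instead.)

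**2. Route to the endpoint.** A 5% marrow gives CR only if counts recover and there are no circulating blasts, Auer rods or extramedullary disease. CRi drops the count requirement but keeps the others. MLFS needs only the marrow, and Arm 3 ORR counts MLFS. One patient among 30 is 1/30 = 3.3 percentage points.

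**3. Reproducing the plan's figures (Arm 3 salvage, section 11.3 E).** Inputs: response prior Beta(0.5, 1.5), response threshold 0.25 + 0.35 = 0.60, cut-off 0.975. The rule is to stop after r responses in n patients if P(p < 0.60) > 0.975, where p follows Beta(0.5 + r, 1.5 + n − r). This gives stopping at 1, 3, 5, 8 and 10 responses or fewer at n = 5, 10, 15, 20 and 25, as printed. The frontline rule, with Beta(1.2, 0.8), threshold 0.80 and cut-off 0.95, gives 2, 5, 9, 12 and 16, also as printed.

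One patient can decide a look. In salvage at n = 10, 3 responses give a posterior probability of 0.986 (stop) and 4 give 0.944 (continue).

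Early stopping was computed exactly from the printed boundaries, with response and toxicity taken as independent:

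P(stop early) = 1 − P(no response stop) × P(no toxicity stop)

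At a toxicity rate of 0.20, P(no toxicity stop) = 0.9854. At ORR 0.60, 1 − 0.8546 × 0.9854 = 0.158 (plan: 0.1579). At ORR 0.45, 1 − 0.4388 × 0.9854 = 0.568 (plan: 0.5676).

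**4. Size under assumed frequencies.** Let f be the share of patients who are responders only because their best marrow was exactly 5%. If ORR is 0.60 with 5% included, it is 0.60 − f under a below-5% rule. The documents give no value for f, so a range is used.

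| Assumed f | ORR at below 5% | P(no response stop) | P(stop early), toxicity 0.20 |
|---|---|---|---|
| 0 | 0.60 | 0.8546 | 15.8% |
| 1% | 0.59 | 0.8368 | 17.5% |
| 3% | 0.57 | 0.7966 | 21.5% |
| 5% | 0.55 | 0.7498 | 26.1% |

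The frontline cohort behaves in the same way at toxicity 0.20: 13.4% at ORR 0.80, 20.9% at 0.77 and 27.0% at 0.75.

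**The case against.** **The two sections serve different purposes.** The Arm 3 marrow rules govern cycle 1 venetoclax and the start of cycle 2. Section 8.1 classifies response, is coherent within itself, and says it modifies the published criteria. Arm 3 ORR covers six months with repeat marrows (section 7.3.6), so a 5% marrow on day 21 or 28 need not settle the endpoint. This stands as a limit on frequency. It does not remove the disagreement over what counts as marrow remission.

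**The comparator.** A reader might infer that the looser cut-off flatters ORR against the 66% frontline benchmark, because section 2.6 describes the venetoclax study with "less than 5% blasts in bone marrow aspirate sample with at least 200 nucleated cells". The documents do not support that. The definition attaches to MLFS only. In those data the ORR was 12 CR + 15 CRi + 1 PR = 28 of 45, with the four MLFS cases listed separately. The 66% benchmark is a CR/CRi rate, and no blast cut-off for CR or CRi is stated for that study. None is stated for the retrospective series behind the salvage benchmark either.

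**Scope.** A reader might extend the point to every arm. In Arms 1 and 2, PR and hematologic improvement also count, so many such patients would be responders under either cut-off.

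**Labels.** A reader might also take the protocol to call 5% persistent disease, or to make it a complete remission outright. It does neither. The Arm 3 rules speak of remission not being confirmed, and CR needs the further criteria.

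**Frequency.** The shares in the table are assumed. At 1% the change in early stopping is under two points.

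**Conclusion.** The contradiction at exactly 5% is in the text, and no section resolves it. It is narrow, and it reaches the primary endpoint mainly in Arm 3, through MLFS. Each affected patient is worth 3.3 ORR points at n = 30 and can move a cohort across a stopping boundary.

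The average effect depends on an unstated frequency. For assumed shares of 1% to 5%, the salvage early-stopping probability differs by about 2 to 10 points (17.5% to 26.1%, against 15.8%). Exact 5% readings are plausible if blasts are reported as whole percentages, which is also an assumption. No bias against either historical benchmark is established. This is a minor point, worth making because the correction costs almost nothing.

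**What to change.** Use one blast cut-off for response scoring in section 8.1. For the Arm 3 primary ORR, score CR, CRp, CRi and MLFS at below 5% marrow blasts, consistent with the protocol's own definition of marrow remission. Move PR (8.1.4) and the blast-response line (8.1.6) to 5% or more, so that an exact 5% is not left outside every category. Report ORR with 5% included as a sensitivity analysis.

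Separately, the sponsor should reconcile the cut-offs in the DLT definition, the Arm 3 marrow rules (5.2.1.7) and the two rules in 5.3.1. No view is offered on which clinical rule is right.

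The cost is a wording change in section 8.1 and one extra line of analysis. The reported ORR may be slightly lower.
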